6. OBJECTIVES AND OUTCOME MEASURES

Objectives	Outcome Measures	Timepoint(s) of evaluation of this outcome measure (if applicable)
Primary Objective To compare the effect of the CMBT-S versus CBT plus standard psychopharmacotherapy for SPD.	
 Change in Personality pathology: Total score at PID-5-BF Schizotypal Personality Disorder Diagnosis: Diagnosis at the 3rd module of SCID-5-PD interview; General Psychopathology: Total score at SCL-90-R; Metacognition: Total score at MAS-A 	9 measurements: (i) at 1 month before intervention starts; (ii) once the treatment starts; (iii) 6 measurements at the end of each month of intervention; at 1-month follow-up; Pre-post evaluation between pre-assessment (1-month before the intervention) and 1-month follow-up assessment.
Secondary Objectives To assess the safety of CMBT-S in patients diagnosed with SPD	
 Dropout rate Completion rate Adverse events (suicidal behaviors, self-harm, psychotic episodes) rate 	At the end of the intervention: dropout rate ($\leq 10\%$ of subjects), completion rate ($\leq 10\%$ of sessions skipped), adverse event rate ($\leq 10\%$ of subjects).

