9.2. Screening and Eligibility Assessment

An assessment psychologist and a psychiatrist conduct an in-depth assessment of demographic and anamnestic variables and integrate them with the results of psychometric tests and structured interviews.

The maximum time between the assessment, the randomization and the start of the course is one month. Protocol waivers are not permitted.

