12. STATISTICS

12.1. Statistical Analysis Plan (SAP)

Primary outcomes will be evaluated through repeated measures ANOVA. Statistical analyses and reporting will be conducted following CONSORT guidelines, with the primary analyses based on the ITT principle, which considered data from all participants whose baseline data were available. Multiple imputation will be adopted to estimate mid-assessment, post-treatment, and follow-up scores for noncompleters (e.g., those who had missed plus than 10% of sessions, or those who decline to participate in the TAU condition). Additionally, we will also conduct per-protocol (PP) analyses, which refers to inclusion in the analysis of only those patients who strictly adhered to the protocol.

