12.2. Sample Size Determination

ANOVA: Repeated measures, within-between interaction has been conducted in order to a priori compute required sample size. As input we estimate ([name], 2020) an effect size f equal to 0.37 with a power $(1-\beta)$ equal to 0.95. Moreover, we considered 9 measurements with at least a correlation among them equal to 0.50 (PID-5-BF reports a test-retest value greater than 0.70). This led to a total sample equal to 12 (critical $F= 2.0563726$; actual power= 0.9785743). By considering at least 10% of withdrawal we

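### The primary test is sized over all nine PID-5-BF scores, with the two earliest used as outcome levels and no baseline or post-treatment contrast named

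*Combined protocol and SAP*

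**What the plan says.** Section 6 (Primary Objective) gives the first outcome as "Change in Personality pathology: Total score at PID-5-BF". It is measured at nine times: "i) at 1 month before intervention starts; (ii) once the treatment starts; (iii) 6 measurements at the end of each month of intervention", plus a score at 1-month follow-up. The score from which change is counted is not named. The same table row contains a "Pre-post evaluation between pre-assessment (1-month before the intervention) and 1-month follow-up assessment", but the Synopsis attaches that window to the secondary outcomes, so it does not settle the reference for PID-5-BF.

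Section 12.1 says: "Primary outcomes will be evaluated through repeated measures ANOVA". It gives no model term, list of occasions, baseline or contrast. Section 12.2 is more specific: "ANOVA: Repeated measures, within-between interaction has been conducted", with "an effect size f equal to 0.37", and "we considered 9 measurements with at least a correlation among them equal to 0.50".

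On the order of events, Section 9.1 randomises participants once eligibility is confirmed, and Section 9.2 says: "The maximum time between the assessment, the randomization and the start of the course is one month". Score (ii), taken at treatment start, therefore comes after randomisation. The text does not say whether it comes before or after the first session.

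**The concern.** The primary objective is to compare the effect of the new therapy with that of the comparator. A reader will want to know whether the arms differ in PID-5-BF after treatment, given where they began, and in whose favour. A nine-level group-by-time interaction asks something wider: whether the two mean profiles fail to be parallel anywhere. Scores (i) and (ii) are then two of the nine outcome levels, although their natural use in a trial of 14 people is as a baseline that sharpens the comparison. With no baseline or contrast fixed in advance, the reading of a significant interaction, and the reference point for change, would be settled after the data are seen.

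**Working it through.** **1. Reproduce the sizing.** Inputs from Section 12.2: f = 0.37, m = 9 occasions, correlation r = 0.50, N = 12. Two arms at 1:1 come from Section 7. Alpha is not stated; 0.05 is inferred because it returns the stated critical F.

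- Noncentrality: λ = f²·N·m/(1−r) = 0.1369 × 12 × 9 / 0.5 = 29.57.
- Degrees of freedom: (2−1)(9−1) = 8 and (12−2)(9−1) = 80.
- 0.95 quantile of F(8, 80) = 2.05637; power = 0.97857.

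Both match the stated 2.0563726 and 0.9785743. The sized test is therefore the 8-df interaction over all nine scores.

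**2. What the test responds to.** Let d be the between-arm difference at each occasion in SD units, and S the sum of squares of d about its own mean over the nine occasions. Then λ = (N/4)·S/(1−r).

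A difference x at one occasion only gives S = x²(1 − 1/9) = 0.889x², whichever occasion it is. A difference at treatment start alone thus counts exactly as much as the same difference at follow-up alone. The sign of x drops out, so the test has no direction.

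**3. Size of the effect on interpretation.** Assume a difference at score (ii) only, N = 14 (Synopsis), equal correlations, alpha 0.05, F(8, 96). At 0.5 SD and r = 0.5, for example, λ = 3.5 × 0.25 × 0.889 / 0.5 = 1.56.

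| Difference at (ii) only | r = 0.5 | r = 0.7 |
|---|---|---|
| none | about 5% | about 5% |
| 0.25 SD | 6.2% | 7.1% |
| 0.5 SD | 10.5% | 15.1% |
| 1 SD | 34% | 57% |

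The documents give no SD and no expected lead-in change, so the size of the shift is an assumption.

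**4. What a baseline-adjusted contrast would give.** Take the mean of k post-treatment scores, adjusted for the mean of (i) and (ii). With equal correlations its residual variance is V = r + (1−r)/k − 2r²/(1+r). At r = 0.5:

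- month 6 and follow-up (k = 2): 0.75 − 0.333 = 0.417;
- all seven later scores (k = 7): 0.571 − 0.333 = 0.238.

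Two assumed profiles are scaled to the plan's f = 0.37, so that S = 4·m·f² = 36 × 0.1369 = 4.93:

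- *Steady ramp* (0, 0, then equal steps to 1 at month 6, then 1). S per unit is 1.278, so the difference reaches √(4.93/1.278) = 1.96 SD.
- *Early response that partly converges* (0, 0, .5, 1, 1, 1, .8, .6, .5). S per unit is 1.26, so the peak is √(4.93/1.26) = 1.98 SD.

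The approximate noncentrality is the contrast difference divided by √(4V/N), on 12 − 3 = 9 error df. For the ramp with month 6 and follow-up it is 1.96/√(0.417/3) = 5.3. For the early response it is 1.98 × 0.55/√(0.417/3) = 2.9. Simulated power at N = 12, r = 0.5:

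| Analysis | Ramp | Early response |
|---|---|---|
| Nine-level interaction | 98% | 98% |
| Mean of month 6 and follow-up, adjusted | 99% | about 70% |
| Mean of seven later scores, adjusted | 96% | 99% |

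**The case against.** The strongest reply is that randomisation protects the test, and that part stands. Lead-in change common to both arms cancels in the interaction. With no arm difference at any occasion, simulation under equal correlations gives 5.1% rejection with nine scores and 5.0% when the month -1 score is dropped. A reader might infer that the early scores bias the comparison or inflate false positives; they do not. Assumed serial correlation of 0.7 to 0.9 without a sphericity correction does raise the null rate to about 9% to 12%, but similarly with eight or nine scores, so that is a separate matter.

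A reader might also infer that the plan declares the lead-in month to be treatment time. It does not: Section 12.1 gives that month no role at all, and the nine levels come from the sizing in Section 12.2. The inference is strong, since the critical F fits, but it remains an inference.

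Section 9.5 states that participants, care providers and assessors are blinded, and Section 7 calls the randomisation double-blind. On that text, a shift at score (ii) from learning the allocation should not occur. The figures in step 3 show what the test would respond to; they do not predict that such a shift will happen.

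Finally, a difference confined to the treatment months is a real difference between therapies under way. It would be wrong to count significance from it as spurious. Whether early response or end state matters more is a choice for the sponsor, which is why that choice should be written down.

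**Conclusion.** The concern holds as a gap in specification and a poor use of data already collected. The sized test uses all nine scores as outcome levels, has no direction, and cannot show whether the arms differ after treatment relative to before it; no baseline or primary contrast is named. A significant result would therefore not by itself answer the primary objective. The illustration, 10.5% to 15% at 0.5 SD and 34% to 57% at 1 SD for a difference at treatment start alone, rests on assumed shifts, equal correlations of 0.5 to 0.7, and N = 14. It does not show that the type I error is wrong or that blinding fails. The change should be made before analysis, but it is not a fatal fault. The title's non-inferiority aim, for which no margin is given, is a separate problem that this point does not resolve.

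**What to change.** 1. **Section 6:** state that score (ii) is taken before the first session.
2. **Section 12.1:** stop using (i) and (ii) as outcome times. Use their mean as the baseline covariate if (ii) is taken before the first session and before the participant can know the allocation; otherwise use (i) alone.
3. **Section 12.1:** prespecify one between-arm, baseline-adjusted comparison of post-treatment PID-5-BF as primary. Options are the mean of month 6 and follow-up if the end state is the question, or the mean of all seven later scores if early response also matters. Report the monthly profile as supportive.
4. **Section 12.2:** restate power for the chosen contrast.

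This needs no new visit, instrument or participant. It costs one degree of freedom for the covariate, and power comes to depend on the contrast. In the two profiles examined, the seven-score mean stays at 96% or above, whereas the month 6 and follow-up mean falls to about 70% if an early response partly converges. Using (i) alone leaves a larger residual variance, V = r + (1−r)/k − r², which at r = 0.5 is 0.50 rather than 0.417 for k = 2 and 0.321 rather than 0.238 for k = 7. Power would be lower accordingly.

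### SCL-90-R and MAS-A have no baseline-adjusted analysis; if the ANOVA of 12.1 covers them it compares change scores, and ANCOVA on the pre-assessment score would remove chance imbalance

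*Combined protocol and SAP*

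**What the plan says.** Section 6 (Objectives and Outcome Measures) lists "General Psychopathology: Total score at SCL-90-R; Metacognition: Total score at MAS-A" under the Primary Objective, with the timing "Pre-post evaluation between pre-assessment (1-month before the intervention) and 1-month follow-up assessment". The synopsis (Section 3) gives the same two time points but puts both scales in the Secondary row and keeps only the PID-5-BF as primary.

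Section 12.1 names one method: "Primary outcomes will be evaluated through repeated measures ANOVA". It mentions no covariate or baseline adjustment, and no method for secondary outcomes. Section 12.2 shows which term of the ANOVA the planners had in mind: "ANOVA: Repeated measures, within-between interaction has been conducted in order to a priori compute required sample size".

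The sample size is 14 (synopsis), allocated 1:1 (Section 7). Section 9.4 describes a computer-generated random number for each participant, without stratification or balancing on baseline scores. Sections 7 and 9.2 put assessment before randomisation.

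**The concern.** With only two time points, the group-by-time test of a repeated measures ANOVA is the same test as a t test comparing change scores between arms. A change score fixes the slope of follow-up on baseline at 1. When the true slope is r, which is below 1, the arm that happened to start worse is expected to improve more through regression to the mean alone. Arms of about 7, randomised without balancing, will often differ noticeably at baseline.

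At stake are the estimated arm differences on two supporting scales. Each can be shifted by the imbalance that happens to occur, and each may have a wider interval than necessary, although a covariate already collected could be used.

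**Working it through.** **Inputs.** N = 14, 1:1, so about 7 per arm (synopsis; Section 7). Two time points (Sections 3 and 6). Alpha is not stated; the critical F in 12.2 implies 0.05. The pre-post correlation r is not given for either scale. Section 12.2 has "9 measurements with at least a correlation among them equal to 0.50" and "PID-5-BF reports a test-retest value greater than 0.70", which are lower bounds and concern the PID-5-BF only. I therefore assume r and show 0.5 to 0.9. Equal SDs at the two time points are assumed, and results are in SD units.

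**1. The plan's own figure.** Section 12.2 uses "an effect size f equal to 0.37 with a power" of 0.95. With two groups and m = 9 measurements:
- lambda = f² × N × m / (1 - rho) = 0.1369 × 12 × 9 / 0.5 = 29.57
- df1 = 1 × 8 = 8; df2 = (12 - 2) × 8 = 80
- critical F = 2.05637; power = 0.97857 (under sphericity)

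This matches "critical $F= 2.0563726$; actual power= 0.9785743". N = 10 gives 0.941, below the target. Allowing for 10% withdrawal, 12/0.9 = 13.3, so 14. The calculation is correct on its inputs, but it describes nine PID-5-BF measurements, not two measurements of SCL-90-R or MAS-A.

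**2. The identity.** In a simulated 7 + 7 data set with two time points, the group-by-time F was 1.0454 and the squared change-score t was 1.0454.

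**3. Chance imbalance.** The SD of the baseline mean difference is sqrt(2/7) = 0.53. The probability that it exceeds 0.5 in absolute value is P(|Z| > 0.5/0.5345) = 0.35.

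**4. How much reaches the estimate.** Given a baseline difference D, the change-score estimate shifts by (1 - r) × D in the opposite direction. For a one-SD imbalance of 0.53 that is 0.27 at r = 0.5 and 0.16 at r = 0.7. In 40,000 simulated trials per setting, among those with D above 0.5 in one direction, the change-score estimate was off by 0.40, 0.23, 0.16 and 0.08 at r = 0.5, 0.7, 0.8 and 0.9. The ANCOVA estimate was off by about 0 throughout. Over all simulated trials, type I error was about 5% for both methods.

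**5. Precision.** Change-score variance is proportional to 2(1 - r) and ANCOVA variance to (1 - r²), a ratio of (1 + r)/2. Estimating the slope multiplies this by 1 + 1/(N - 4), which is 1.10 at N = 14 and 1.125 with 12 completers. Interval width also reflects the change from t on N - 2 to t on N - 3 degrees of freedom.

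| r (assumed) | Variance ratio, N = 14 | CI width ratio, N = 14 | Variance ratio, N = 12 | CI width ratio, N = 12 |
|---|---|---|---|---|
| 0.5 | 0.75 × 1.10 = 0.825 | 0.918 | 0.844 | 0.933 |
| 0.7 | 0.85 × 1.10 = 0.935 | 0.977 | 0.956 | 0.993 |
| 0.8 | 0.90 × 1.10 = 0.990 | 1.005 | 1.012 | 1.022 |
| 0.9 | 0.95 × 1.10 = 1.045 | 1.033 | 1.069 | 1.050 |

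The simulated variance ratios at N = 14 were 0.829, 0.934, 0.990 and 1.049. Variance breaks even at r = 2/1.10 - 1 = 0.82 (N = 14) and 2/1.125 - 1 = 0.78 (N = 12). Interval width breaks even near 0.78 and 0.72.

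**6. Power.** For a true difference of 1.2 SD, which is my assumption and appears nowhere in the documents, power at N = 14 for change score versus ANCOVA is 54% versus 62% at r = 0.5, 75% versus 78% at 0.7, 90% versus 90% at 0.8, and 99.6% versus 99.3% at 0.9.

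**The case against.** The best defence is that the plan may never have intended a change-score test for these scales. Section 12.1 confines the ANOVA to primary outcomes, and the synopsis calls both scales secondary. This stands: the change-score analysis follows only on the Section 6 reading. On the synopsis reading there is no stated method at all. The plural in 12.1 fits Section 6 better, since the synopsis has a single primary measure, but that does not settle it. Either way a sentence on the analysis is missing.

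Second, a change-score comparison is a legitimate method. Averaged over randomisations it is unbiased and holds its type I error. This stands too. A reader might infer that the planned analysis is biased or invalid, but it is not: the shift is conditional on the imbalance that occurs.

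Third, the precision gain is modest and can reverse. This also stands. A reader might infer that ANCOVA is always the more precise choice; in a trial of 12 to 14 it is not once r passes roughly 0.7 to 0.8. Nor do the PID-5-BF values cap r at 0.70 for these scales, since they are lower bounds for a different instrument. The two assessments are about eight months apart (1 + 6 + 1), which makes a moderate r plausible, but the documents do not establish it.

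What the defence leaves untouched is the conditional shift, which ANCOVA removes at any r in the table, including where precision no longer differs.

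**Conclusion.** The point holds as a worthwhile, inexpensive improvement. If 12.1 governs SCL-90-R and MAS-A, they will be compared on change scores without baseline adjustment. In a trial where about 35% of randomisations would leave the arms more than 0.5 SD apart on a given scale, that carries (1 - r) of the gap into the result. Baseline adjustment removes this at any r. On precision, it shortens the interval by about 8% at r = 0.5 and 2% at r = 0.7, makes no practical difference near 0.8, and lengthens it by about 3% at 0.9, all at N = 14. These figures rest on an assumed r, equal SDs and arms of 7. None of this calls the stated sample size into question.

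**What to change.** In 12.1, state that SCL-90-R total and MAS-A total at 1-month follow-up will each be compared between arms by ANCOVA with the pre-assessment score of the same scale as covariate, reporting the adjusted difference and its 95% CI, and that within-arm pre-post changes are descriptive only. Reconcile the synopsis with Section 6 on whether the two scales are primary or secondary.

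The cost is the added wording, one residual degree of freedom and, if r is near 0.9, intervals about 3% wider (5% with 12 completers). No new data are needed: the covariate comes from the pre-assessment, and 12.1 already defines the ITT set by available baseline data. Fixing the method in advance also prevents a choice between change scores and adjustment after the imbalance has been seen.

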3. SYNOPSIS

Trial Title	Compassion and Metacognition Based Therapy for Schizotypal Personality Disorder: A Pilot Non-inferiority Randomized Controlled Trial on Repeated Measures.
Internal ref. no. (or short title)	Compassion and Metacognition in Schizotypal Personality (CMBT).
Trial registration	Unique Protocol ID: 03-07072020
Sponsor	Tages Onlus [name]
Funder	N/A
Clinical Phase	Recruiting
Trial Design	Parallel Assignment Randomized Controlled Trial with Repeated Measures
Trial Participants	Minimum Age: 18 Years Being diagnosed with Schizotypal Personality Disorder at SCID-5-AMPD
Sample Size	14
Planned Trial Period	Total lenght: December 15, 2020 - December 20, 2021

	Pre-post evaluation between pre-assessment (1-month before the intervention) and 1 month follow-up.		
Planned Recruitment period	December 15, 2020 - September 30, 2021		
	Objectives	Outcome Measures	Timepoint(s)
Primary		Personality pathology: Total score at PID-5-BF	(i) at 1 month before intervention starts; (ii) once the treatment starts; (iii) 6 measurements at the end of each month of intervention; at 1-month follow-up.
Secondary		Schizotypal Personality Disorder Diagnosis: Diagnosis at the 3rd module of SCID-5-PD interview; General Psychopathology: Total score at SCL-90-R; Metacognition: Total score at MAS-A	Pre-post evaluation between pre-assessment (1-month before the intervention) and 1-month follow-up assessment.
Intervention(s)	
 IMP(s) nIMP(s) Other intervention(s) 	Compassion and Metacognition Based Therapy (CMBT): Third Wave Cognitive Therapy targeting metacognitive dysfunctions (through Metacognitively Oriented Psychotherapy) and selfcriticism (through Compassion Focused Therapy). 6-month therapy, including 24 weekly sessions.	
Comparator	Cognitive Behavioral Therapy: Standard Cognitive Behavioral Therapy for Personality Disorders plus Standard Psychopharmacological Treatment. 6-month therapy, including 24 weekly sessions.		

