7. TRIAL DESIGN

Randomized Controlled Trial with Repeated Measures.

After being informed about the study and potential risks, all patients giving written informed consent will undergo a psychological assessment so as to determine eligibility for study entry. Patients who meet the eligibility requirements will be randomized in a double-blind manner in a 1:1 ratio to new integrative

psychotherapy or treatment as usual (cognitive behavioral therapy plus standard psychopharmacological treatment). One month after the conclusion of the two forms of treatment (both lasting 6 months), patients will have access to the final follow-up assessment.

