11. SAFETY REPORTING

11.1. Adverse Event Definitions

Adverse Event (AE)	Any untoward medical occurrence in a participant to whom the intervention has been administered, including occurrences which are not necessarily caused by or related to that treatment.
Serious Adverse Event (SAE)	
A serious adverse event is any untoward medical occurrence that:
 
• results in death• is life-threatening• requires inpatient hospitalisation or prolongation of existing hospitalisation• results in persistent or significant disability/incapacity• consists of a congenital anomaly or birth defect*. 
Other 'important medical events' may also be considered a serious adverse event when, based upon appropriate medical judgement, the event may jeopardise the participant and may require medical or surgical intervention to prevent one of the outcomes listed above.
 
NOTE: The term "life-threatening" in the definition of "serious" refers to an event in which the participant was at risk of death at the time of the event; it does not refer to an event which hypothetically might have caused death if it were more severe.

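### The adverse event rate, with its 10% limit, closes at the end of the intervention, so a listed event in the follow-up month falls outside the trial's stated safety outcome

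*Combined protocol and SAP*

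**What the plan says.** The table in section 6 gives one secondary objective, "To assess the safety of CMBT-S in patients diagnosed with SPD". It has three outcomes: dropout, session completion and "Adverse events (suicidal behaviors, self-harm, psychotic episodes) rate". All three share a single timepoint, which opens "At the end of the intervention: dropout rate" and continues with the other two. The adverse event rate carries a limit of 10% of subjects.

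Efficacy runs a month longer. Section 7 states: "One month after the conclusion of the two forms of treatment (both lasting 6 months), patients will have access to the final follow-up assessment". The Synopsis gives the secondary efficacy outcomes (SCID-5-PD diagnosis, SCL-90-R, MAS-A) as a "Pre-post evaluation between pre-assessment (1-month before the intervention) and 1-month follow-up assessment", and the last of the nine PID-5-BF measurements is taken at the same visit.

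Two other places bear on safety. Section 11.1 defines an adverse event as "Any untoward medical occurrence in a participant to whom the intervention has been administered", with no time limit. Section 14.3.1 has the sponsor review SAEs quarterly and cumulatively, with no start or end of collection stated. Neither changes the timepoint of the section 6 rate.

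**The concern.** Patients remain in the trial for a month after therapy stops, and efficacy is measured at the end of that month, but the adverse event rate closes before it. The three listed events are the ones on which the trial proposes to judge safety. If one occurs two weeks after the last session, the rate compared with 10% does not include it. The trial would then report efficacy over seven months from treatment start and safety over six. With arms this small, one patient can decide whether the limit is met.

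A related gap concerns retention. The only post-treatment SCID-5-PD, SCL-90-R and MAS-A values come from the follow-up visit, and no stated outcome counts patients who finish therapy but miss it.

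**Working it through.** **Inputs.** Treatment lasts 6 months and follow-up is 1 month later (sections 6 and 7). The planned sample is 14 (Synopsis), allocated 1:1 (section 7), so about 7 per arm. The limit is 10% of subjects (section 6).

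**The plan's own sample size.** Section 12.2 gives f = 0.37, 9 measurements and correlation 0.50. Alpha is not stated; 0.05 is assumed.
- Noncentrality: f² × N × m / (1 − ρ) = 0.37² × 12 × 9 / 0.50 = 29.57, with 8 and 80 degrees of freedom.
- Critical F = 2.0563726 and power = 0.9785743, both as stated, which supports the assumed alpha.
- 12 / 0.90 = 13.3, rounded up to 14, the planned number.

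This confirms the 14. It does not depend on the safety window and does not change if the window does.

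**Share of time left out.** 1 of 7 months after treatment start: 1/7 = 14.3%.

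**What the limit allows.**
- Arm of 7: 0/7 = 0% meets the limit; 1/7 = 14.3% misses it.
- All 14 pooled: 1/14 = 7.1% meets it; 2/14 = 14.3% misses it.
- Exactly 7 is not essential. 1/n exceeds 10% for any arm below 10 patients (1/9 = 11.1%), so an uneven split gives the same answer unless the arm reaches 10.

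For an arm of 7 with no earlier event, one patient in the follow-up month moves the rate from 0% to 14.3%. Pooled, the result changes only if that patient is the second.

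**How often the window decides the result.** The documents give no event rate, so the 6-month risk p₆ is an assumption, shown over a range, with a constant hazard. The 7-month risk is p₇ = 1 − (1 − p₆)^(7/6). The chance that an arm of 7 meets the limit is (1 − p)⁷; for 14 pooled it is the binomial chance of 0 or 1 patients.

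| Assumed 6-month risk | 7-month risk | Arm of 7 meets limit, 6 → 7 months | Pooled 14 meets limit, 6 → 7 months |
|---|---|---|---|
| 5% | 5.8% | 69.8% → 65.8% | 84.7% → 80.6% |
| 10% | 11.6% | 47.8% → 42.3% | 58.5% → 50.7% |
| 20% | 22.9% | 21.0% → 16.2% | 19.8% → 13.5% |
| 30% | 34.0% | 8.2% → 5.4% | 4.7% → 2.4% |

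The difference within each pair is the chance that the extra month changes the verdict: about 3 to 6 percentage points for an arm of 7, and about 2 to 8 pooled.

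**The case against.** The strongest reply is that post-treatment events are not lost. Section 14.3.1 reviews SAEs cumulatively with no cut-off at the end of therapy, and under section 11.1 an event that is life-threatening or needs inpatient admission is an SAE. A serious event in the seventh month therefore has a route to review. This stands, and it rules out the inference that the trial ignores such events. It does not close the gap: the review covers serious events only, states no collection window, and is not linked to the 10% limit.

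A reader might also see a contradiction between sections 6 and 11.1. There is none. A general definition without a time limit can coexist with a rate evaluated at a stated time.

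On dropout, a reader might infer that someone who finishes therapy and misses follow-up is counted as retained, so the dropout window must also be extended. The documents do not say this. Dropout is undefined, section 9.6 separates stopping treatment from staying in follow-up, and treatment dropout is complete when treatment ends. Merging it with loss to follow-up would blur both. What remains is narrower. The imputation rule in section 12.1 is written for noncompleters, exemplified by missed sessions or declining the comparator condition. It does not expressly cover a completer who misses follow-up.

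Finally, 1/7 = 14.3% reflects arm size and would apply to one event in any month. This is correct, and the table above is the better measure of what the window itself does.

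**Conclusion.** The point holds for the adverse event rate. As written, suicidal behaviour, self-harm or a psychotic episode in the follow-up month is outside the stated safety outcome, and no other section brings it in.

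The size is conditional. One such patient turns a met limit into a missed one only if the limit applies to the CMBT-S arm, that arm has fewer than 10 patients, and no earlier patient had an event. The objective names CMBT-S, which favours the per-arm reading, but the plan does not say so. Pooled over 14, a single event leaves the limit met at 7.1%. It would therefore be too strong to say that any uncounted case breaks the criterion. Under the assumed risks, the chance that the extra month changes the verdict is modest.

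Nor do the documents show that the month after therapy carries a raised risk. The argument needs only that patients are still in the trial and that including the month costs little.

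**What to change.** In section 6:

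- Count the adverse event rate from treatment start to the 1-month follow-up, in both arms. Treatment start is preferable to randomisation because section 11.1 limits adverse events to participants who have received the intervention, and section 9.2 allows up to a month between assessment, randomisation and start.
- Ask about the three listed events at the existing monthly assessments and at the follow-up visit. No section currently schedules this enquiry.
- Report during-treatment and follow-up-month figures separately by arm, and state whether the 10% limit applies to the CMBT-S arm or to all participants.
- Keep treatment dropout and session completion at the end of the intervention. Report loss before the 1-month follow-up as its own figure, by arm.

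This adds no visits and leaves the sample size and the treatments unchanged. The cost is a short question at assessments already planned, and a reported event rate that may be slightly higher.
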